We will layer data collection and the implementation of the combined-care model and social media campaign over three phases. Phase 1 is the pre-intervention phase and it will last for 4 months (months 1-4). The only study activity during the pre-intervention phase is the collection of routine PrEP uptake data to establish a baseline for PrEP prescribing at the GYN residency clinics and local PrEP clinics. Phase 2 is the implementation of the combined-care model at the LSU GYN residency clinic at UMCNO for 4 months (months 5-8). Phase 3 adds implementation of the social media campaign in the NOLA area for 4 months (months 9-12); implementation of the combined-care model at LSU GYN residency clinic at UMCNO will continue during this time (Figure 1). The layered approach allows for an opportunity to assess the effect of the combined-care model, and subsequently, to what extent the social media campaign additionally engages Black women and builds demand for PrEP.

We also include a comparator arm to evaluate changes in PrEP uptake due to other secular trends in the area and increases due to the social media campaign. The three comparator clinics are: (1) another GYN resident program (Tulane Downtown GYN Clinic), (2) the UMCNO PrEP clinic ([name], PI, is a provider), and the Tulane PrEP clinic.

5. Study Outcomes

We will assess both implementation outcomes (Table 1) and clinical outcomes (Table 2).

The implementation outcomes are guided by Proctor et al and include: acceptability, feasibility, appropriateness, adoption, fidelity, and maintenance.⁵ These outcomes will be assessed qualitatively through in-depth interviews (IDIs), debriefing sessions with GYN residents and leadership, medical chart reviews and/or de-identified Epic queries, training records, discussions with the BWAP Task Force, and social media metrics.

Table 1: Implementation Outcomes		
Outcomes	Measurement	Data sources & level of analysis
Acceptability	Satisfaction of complexity, content, relative advantage, and credibility of implementation strategies being delivered.	Provider: Debriefing sessions & IDIs Patient: IDIs Community stakeholders: Regular meeting with the BWAP Task Force
Feasibility	Fit from site perspective, suitability for everyday use, practicability.	Provider: Debriefing sessions & IDIs

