Appropriateness	Perceived fit and relevance to needs of Black cisgender women and suitability for GYN residents to implement	Provider: Debriefing sessions & IDIs Patient: IDIs Community stakeholders: Regular meeting with the BWAP Task Force
Adoption	
 • # residents trained/# residents rotating through GYN clinic • # residents initiating PrEP/# residents rotating through GYN clinic • Time between training providers & their beginning to implement 	Provider: Training records, chart review
Fidelity	
 • Time to implement: Average response time from social media inquiries by PrEP navigator • Completeness of combined care model delivery per eligible clients (% discussed PrEP; % provided PrEP counseling; % made a PrEP follow up plan; # monthly feedback sessions occurring) • Quality of implementation strategy delivery • Consistency of fidelity within and across providers 	Social media: Records of inquiries, calls and responses; metrics (e.g., post frequency, specific post reach, likes and amplification rates as a marker of quality) Provider: Epic data pull, chart review (completion/consistency); IDIs (quality) Patient: IDIs (quality)
Maintenance	
 • Adoption (see above) by providers over time • Fidelity of completeness (see above) of delivery over time 	Provider: Epic data pull, chart review
Reach	
 • # social media video views; # jingle plays; # campaign Facebook site visits 	Social media: Platform metrics (e.g. Facebook, TikTok)

Table 2: Clinical outcomes, primary and secondary	
Primary	
 • Total number of women overall and number of Black cisgender women initiating PrEP at the LSU GYN clinic during the pre-implementation period (Phase 1: months 1-4) compared to during the two implementation period phases (Phase 2: months 5-8 and Phase 3: months 9-12). • Comparison of the difference in patient numbers at the LSU GYN clinic during pre-implementation and the two implementation period phases with the difference in patient numbers during the same time frame at the Tulane GYN clinic. • Comparison of the difference in patient numbers at LSU GYN clinic and UMC PrEP clinic combined to the Tulane GYN and Tulane PrEP clinics combined during the same time frame to further investigate trends outside of the GYN clinics potentially impacted by the social media campaign.

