LSU GYN residents and leadership: We aim to interview a diverse group of LSU GYN residents based on their varying experiences in starting a PrEP conversation with patients and prescribing PrEP. We will work with the residency program’s PrEP leadership to identify and purposefully select residents to invite for the IDIs. This will be coupled with Epic data pull reviews to document adoption and fidelity of provider implementation during the pilot. Adoption and fidelity outcomes will be summarized by provider, including the number of PrEP conversations started and the number of PrEP prescriptions provided by patient demographics (i.e., race and age). Any patient information will be de-identified, and the list provided to study staff. We will aim to purposefully select (1) three residents who frequently started a PrEP conversation but did not prescribe PrEP, (2) three residents who infrequently started a PrEP conversation, and (3) three residents who frequently prescribed PrEP. Modifications in our selection process may be needed based on the number of residents who start a PrEP conversation or prescribe PrEP. Study staff will contact each selected resident to invite them to participate in an IDI. Interested residents will be connected to study staff to receive an information sheet about the study and scheduling. We will also interview members of the GYN leadership team, such as attending preceptors and the LSU GYN residency program director(s).

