We will conduct monthly feedback sessions throughout the study (e.g., at the end of each month-long rotation) with the LSU GYN residents and leadership. The purpose is to discuss their experiences with implementing the *Start the Conversation* initiative and make adaptations to the combined-care model (e.g. adjustments, additions and/or subtractions of action steps) as needed. The residents will receive information regarding their fidelity during the end of month feedback session and will have an opportunity to provide suggestions of components to change, add, or subtract to increase feasibility and acceptability. Residents and leadership will be informed that we will use information discussed at these meetings for research purposes (e.g., describing adaptations made during research dissemination). We will also use Epic data pulls of extractable data elements as needed to inform components that may need adaptation (e.g. was a PrEP conversation initiated, were shared decision-making talking points used).

8. Data analysis

We will evaluate the primary clinical outcomes using a difference-in-differences approach⁶ to account for changes within time periods (pre- and post-implementation) and across sites (LSU versus Tulane). Poisson regression will be used to determine synergistic effects of the social media layering using weekly PrEP initiation counts, comparing uptake across implementation periods and sites and employing a product term to assess the impact of jointly implementing the combined-care model and social media campaign. We will analyze the secondary clinical outcomes using descriptive statistics.

We will use thematic analysis to analyze the qualitative data from the IDIs. Informed by the Proctor outcomes⁵ and the Consolidated Framework for Implementation Research,⁷ analysts will first develop a structural codebook based on predetermined topics explored during data collection. Next, content codes will be developed to capture emergent content. Transcripts will be coded by two or more analysts. Analysts will conduct inter-coder reliability assessments on approximately 25% of the transcripts; discrepancies will be resolved through discussion, codebooks will be updated as appropriate, and subsequent text will be recoded as needed.

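### Residents' views on acceptability, feasibility and appropriateness are gathered in sessions that include their leadership and give fidelity feedback, which leaves them open to social desirability

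*Protocol*

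**What the plan says.** Section 5 states that the implementation outcomes are assessed qualitatively, with sources that include "debriefing sessions with GYN residents and leadership". In Table 1 the provider entry for acceptability, feasibility and appropriateness is "Provider: Debriefing sessions & IDIs". Acceptability and appropriateness also list patient interviews and meetings with the BWAP Task Force. Feasibility lists nothing else.

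Section 7 provides for monthly feedback sessions "with the LSU GYN residents and leadership", for instance at the end of each rotation. On fidelity it says: "The residents will receive information regarding their fidelity during the end of month feedback session". At that session residents can also suggest changes that would raise feasibility and acceptability. Attendees are told that "we will use information discussed at these meetings for research purposes".

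Section 6 (In-depth interviews) says: "We will work with the residency program’s PrEP leadership to identify and purposefully select residents to invite for the IDIs". Selection is tied to Epic summaries of adoption and fidelity by provider, and three groups of three residents are named. The same section gives attending preceptors and residency program directors as examples of the GYN leadership team, whose members are also interviewed.

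Section 10 (Chart reviews) assures residents that their standing does not depend on whether, or how consistently, they implement the model.

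**The concern.** A trainee asked whether a new care model is practical, with a preceptor or program director present and in the meeting where fidelity is reported, has a reason to hold back criticism. A resident who rarely used the model has the most reason. If that happens, the provider evidence on the three outcomes leans favourable. Evaluating implementation outcomes is the first objective in Section 2, so this evidence is central to the pilot. A barrier that residents do not voice also cannot inform the adaptations that Section 7 is meant to produce.

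**Working it through.** No test, power or sample-size figure underlies this point. The check sets the relevant sections side by side, with simple counts.

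**1. Sources for each outcome (Table 1).**

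| Outcome | Provider sources | Other sources |
|---|---|---|
| Acceptability | Debriefings, interviews | Patient interviews, Task Force |
| Feasibility | Debriefings, interviews | None |
| Appropriateness | Debriefings, interviews | Patient interviews, Task Force |

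These are 3 of the 7 outcomes in Table 1. Only feasibility rests wholly on providers.

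**2. Size of the sessions.** Implementation runs over months 5 to 12 (Section 4), which is 8 months and so about 8 monthly sessions. Section 3 expects about 4 to 6 residents per monthly training. 8 × 4 = 32 and 8 × 6 = 48, which reproduces the 32 to 48 trained residents in Section 6. If the feedback group is the training group, each session holds about 4 to 6 residents, so individual views are easy to attribute.

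**3. Protection in the sessions.**
- Attendance: residents and leadership are named together. No residents-only part or anonymous form is described.
- Feedback: fidelity information is given in the session at which suggestions are invited.
- Assurance: the statement on standing sits under Chart reviews in Section 10 and concerns implementing the model. The assurance about declining an interview, also in Section 10, refers to health care, which does not address a trainee's evaluation. Neither covers what residents say.

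**4. Protection in the interviews.**
- Invitation: made by study staff, who also handle information and scheduling (Section 6).
- Setting: Zoom or telephone, with the interviewer in a private location (Sections 6 and 10).
- Records: transcripts carry a code, and the identity log is password-protected with limited access (Section 10).
- Selection rule: 3 + 3 + 3 = 9 named places out of 12 residents, leaving 12 − 9 = 3 with no stated criterion. Of the 9, 3 go to residents who start conversations without prescribing and 3 to those who seldom start one: 6 / 9 = 67%. Frequent prescribers have 3 / 9 = 33%.

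The written rule therefore does not tilt toward favourable respondents. What remains is that PrEP leadership takes part in choosing and so may know who was chosen and from which performance group. Study staff already receive the by-provider list, so the documents show no need for that involvement.

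**The case against.** A reader might infer that both provider sources run through the residents' supervisors and that the results are pushed upward. The documents do not support that.

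- Leadership touches the interviews only at selection, and two thirds of the named places go to non-prescribers or low users. Nothing says that leadership hears an interview or sees a transcript.
- The group that helps select is called the program's PrEP leadership. The Protocol does not say that it consists of the preceptors and directors named elsewhere, or that it assesses residents.
- There are no rating scales to inflate. The outcomes are qualitative and the interviews are analysed thematically.
- Not all provider data are exposed, because leadership members are interviewed in their own right and trainee deference does not apply to them.

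On the sessions, the other side can say that debriefings and monthly feedback meetings are never expressly equated, that fidelity might be shown only for the group, and that residents are openly invited to propose changes. Feasibility is defined from the site's perspective, so leadership has a proper place in the discussion. Adoption, fidelity and maintenance draw on training, Epic or chart records, which give a behavioural check on use.

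Most of this stands, and it narrows the point to the sessions plus one selection step. It does not remove it. The natural reading of Section 7 is a joint meeting, records of use do not show why residents find the model hard to use, and no assurance covers what they say.

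**Conclusion.** The concern holds in a limited form. Resident data from the debriefing or monthly feedback sessions are open to social desirability on all three outcomes, and most of all on feasibility. For acceptability and appropriateness, the patient and Task Force sources lessen the consequence. For the resident interviews, the only concern is leadership's part in selection.

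The direction of bias is plausible, but the documents neither show it nor allow its size to be estimated. The conclusion assumes that debriefings and monthly feedback sessions are the same meetings or have the same attendance, that residents and leadership attend together, and that leadership is present when fidelity is reported. The clinical outcomes are untouched. This is an inexpensive improvement to the design and does not invalidate the evaluation.

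**What to change.** - **Section 7:** collect residents' views on acceptability, feasibility and fit in a residents-only segment, or on a short anonymous form, before fidelity results are shown. Leadership then joins for the adaptation discussion.
- **Section 6:** have study staff alone select interview residents from the Epic by-provider summary, without telling leadership who was chosen or from which group.
- **Section 10:** extend the assurance on residents' standing to what they say in sessions and interviews.

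The cost is a split in an existing meeting, slightly more organising and some changes of wording. Leadership hears some resident views second-hand. With about 4 to 6 residents per block, anonymity on a form will be imperfect. Leadership keeps its role in adaptation and its own interviews.

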PrEP combined-care model overview: We will train LSU GYN residents to (1) start the PrEP conversation with all potentially eligible patients (per CDC guidelines), (2) prescribe PrEP for interested patients, and (3) create a plan for PrEP follow up either at the GYN clinic or a local PrEP clinic. Patients will choose whether to receive follow-up care at the LSU GYN resident clinic or be referred to care at a local PrEP provider. We anticipate

providing a monthly training prior to each resident clinic block, with approximately 4 to 6 residents at each training.

[figure not shown]
We may also engage PrEP champions (e.g., a provider or resident at the GYN resident clinic) to follow-up on patients' laboratory assessments and whether they filled their PrEP prescription. The PrEP champion may contact the patient as part of regular patient care.

Social media overview: We will implement a social media campaign focusing on raising awareness about Black cisgender women engaging in PrEP care. The content and strategy were developed as part of our previous protocol (Duke: #Pro00109957; LSU: #2163). Selected members of the BWAP Task Force who are active influencers, other identified influencers, and local organizations will distribute all social media content via their standard channels and approaches for communicating with their followers (e.g., Facebook, TikTok). All social media content will link Black cisgender women to a PrEP navigator located at the Louisiana Department of Health Office of Public Health STD/HIV/Hepatitis Program's (SHHP). SHHP will refer women to a PrEP provider/location of their choice.

4. Study design

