women by date, race, and provider through provider notes. We will also collect data to inform the primary and secondary clinical and implementation outcomes (LSU site only) through Epic data pulls (i.e., provider note templates will incorporate ‘smartlists’ and ‘smartphrases’ with extractable data elements), and if necessary, provider notes and chart review of GYN patients seen. If chart review is required, and depending on the volume of patients seen, we may use a stratified random sampling approach to select patients for the chart review. Additionally, we may also track EMR prescription data to trend PrEP initiations and follow initiation patterns (and thus adoption metrics) across providers for all patients seen during the study period.

We anticipate that 32 to 48 LSU GYN residents will be trained in the combined-care model. The LSU GYN clinic at UMC sees 60 to 80 patients per week; it is estimated that ~30/week will be eligible for PrEP, of which we anticipate ~2 will be initiated per week. This will result in an estimated 2,400 women seen over the 8-months of implementation, of which ~1,000 will be PrEP-eligible and around 70 will take up PrEP in the GYN clinic.

In-depth interviews

We will also conduct IDIs with 12 GYN residents who were trained and 12 patients who were offered PrEP using the “Start the Conversation” guidance and materials.

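### Table 1 takes the PrEP follow-up-plan percentage over all eligible clients, although the plan appears to concern women who accept or start PrEP, so this one fidelity item moves with uptake as well as with resident delivery

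*Protocol*

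**What the plan says.** Protocol section 5, Table 1, Fidelity row: completeness is a measure "of combined care model delivery per eligible clients (% discussed PrEP; % provided PrEP counseling; % made a PrEP follow up plan". The same parenthesis ends with a count of monthly feedback sessions. No separate denominator is given for the plan.

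Protocol section 3 describes the combined-care model in three steps:

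- Step 1: "start the PrEP conversation with all potentially eligible patients (per CDC guidelines"
- Step 2: "prescribe PrEP for interested patients"
- Step 3: "create a plan for PrEP follow up either at the GYN clinic or a local PrEP clinic"

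Steps 1 and 2 name the patients they apply to. Step 3 does not.

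Protocol section 6, In-depth interviews, takes the choice of follow-up location from the list of women who initiated PrEP. Section 6 also gives the expected volumes: weekly, about "30/week will be eligible for PrEP, of which we anticipate ~2 will be initiated per week"; over the eight months of implementation, "of which ~1,000 will be PrEP-eligible and around 70 will take up PrEP in the GYN clinic".

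The completeness measure is used again. The Maintenance row of Table 1 tracks "Fidelity of completeness (see above) of delivery over time", the Fidelity row also asks for consistency within and across providers, and section 7 has residents shown their fidelity at each month-end session.

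**The concern.** A fidelity percentage should approach 100% when the provider does everything that is due. The group narrows through the steps of section 3, from eligible women to interested women, before the plan for follow-up is reached. A woman who has the conversation and declines PrEP appears to have received all that was due to her. Under Table 1 as written she still enters the denominator of the plan item and counts as incomplete delivery.

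The item then answers two questions at once: did the resident make the plan, and did the patient want PrEP? Residents with different patients could differ on it with identical behaviour. A change in uptake between Phases 2 and 3 could look like a change in fidelity. Month-end feedback, which is meant to guide adaptation of the model, could treat refusals as missed steps. The proportion of eligible women starting PrEP is already a secondary outcome in Table 2, so on this denominator the plan item would largely repeat it.

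**Working it through.** **Inputs (protocol section 6).** About 30 eligible women and about 2 initiations per week; about 1,000 eligible and about 70 initiating over eight months; 32 to 48 residents trained.

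**Reproducing the protocol's figures.** Eight months is 8 × 52/12 = 34.7 weeks.

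- Initiations: 2 × 34.7 = 69, against about 70.
- Eligible women: 30 × 34.7 = 1,040, against about 1,000. This is 4% off, and both numbers are marked as approximate.

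The volumes are coherent enough to use.

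**Ceiling if plans are made only for women who start PrEP at the clinic.** Ceiling = initiators / eligible women.

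- Eight-month figures: 70/1,000 = 7.0%
- Weekly figures: 2/30 = 6.7%

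**Ceiling if some other eligible women also receive a plan**, for example by referral without a prescription that day. The protocol gives no count of such women, so their share *s* is an assumption. Ceiling = 0.07 + 0.93 × *s*.

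| Share *s* of other eligible women with a plan (assumed) | Ceiling of the plan item |
|---|---|
| 0% | 7.0% |
| 5% | 11.7% |
| 10% | 16.3% |
| 25% | 30.3% |
| 100% | 100% |

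The denominator in Table 1 is right only in the last row, where every eligible woman is due a plan.

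**Dependence on uptake (assumed uptakes, plans for initiators only).** Item = uptake × share of due plans made.

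- Uptake 7%, all due plans made: 0.07 × 1 = 7%.
- Uptake 14%, half the due plans made: 0.14 × 0.5 = 7%.
- Uptake rising from 2 to 3 per week, all due plans made: 2/30 = 6.7% becomes 3/30 = 10%.

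The first two cases differ twofold in delivery and score the same. In the third, delivery is unchanged and the score rises. Over initiators, the same cases give 100%, 50% and a constant 100%.

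**Per resident.** Spread evenly, 70/48 = 1.5 to 70/32 = 2.2 initiators each. With Poisson variation (an assumption), the chance that a resident has none is exp(−2.19) = 11% to exp(−1.46) = 23%. Such a resident would score 0% on the plan item over eligible clients, however well the model was delivered.

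**The case against.** Several points on the other side have force.

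- **The protocol nowhere says that the plan is only for women taking up PrEP.** Section 3 leaves the group open and allows referral to a local provider. The interview passage describes sampling and does not define the fidelity item. This stands: 7% is the ceiling under one reading, and the range above belongs with it.
- **The heading may be loose.** A count of feedback sessions sits in the same parenthesis and cannot be a percentage of clients, so the phrase on eligible clients may mean eligible for each step. That is possible, but the text does not say so, and the three percentages follow directly on that phrase.
- **Little hangs on the item.** It has no threshold, test or decision rule attached. Initiation among eligible women is reported by phase, and section 6 summarises conversations and prescriptions by provider, so a careful reader could see uptake alongside. This lowers the severity but leaves the item mis-scaled.
- **A Phase 3 rise at this clinic is not assured.** The campaign links women to a state navigator, who refers them to a provider of their choice. This also stands: the move to 10% is an illustration, not a forecast.
- **Exact denominators are often left to an analysis plan.** Here, however, the protocol states one, and it fits the described steps poorly.

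A reader might infer that a perfect resident scores about 7% on completeness as a whole. The document does not support that. It defines no composite score, the same resident would score 100% on the discussion item, and nothing ties counseling to uptake.

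**Conclusion.** The point holds for the follow-up-plan item alone. Over all eligible clients its ceiling is about 7% on the protocol's own volumes if plans are made only for women who start PrEP at the clinic, and about 12% to 30% if 5% to 25% of the other eligible women also receive one (assumed). In either case it depends on patient interest as well as on resident delivery, and that carries into Consistency, Maintenance and the monthly feedback.

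The conclusion rests on reading the plan as a step for women who accept or start PrEP. Section 3 and the interview section indicate this but do not state it. If every eligible woman is meant to leave with a plan, the denominator is right and section 3 should say so. The primary clinical outcomes are not touched. This is a correction worth making to an implementation outcome, not a threat to the main comparison.

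**What to change.** In Table 1, give the items their own denominators:

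- For the percentages discussed and counseled, keep eligible women.
- For the percentage with a follow-up plan, use women prescribed PrEP, adding women referred to a local PrEP provider where the referral is recorded.

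Use the same denominators in Consistency, Maintenance and the month-end feedback, and state in section 3 which women the plan step concerns.

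Counseling should not be moved onto women with whom PrEP was discussed. Section 3 describes no separate counseling step to support this, and a resident who raised PrEP with few women could then score 100%.

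The cost is mainly wording: initiations by provider and extractable note elements are already planned, although capture of referrals without a prescription needs confirming. The statistical cost is a denominator of about 70 instead of about 1,000, hence a wider interval for this item. At roughly 1.5 to 2.2 women per resident, and none for some, it says little about any one resident and is better reported as counts at that level.

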Secondary	
 • Proportion of PrEP-eligible women overall and Black cisgender women initiating PrEP at the LSU GYN clinic across the two implementation time periods (combined-care model only, Phase 2—months 5-8; combined care model plus social media company, Phase 3—months 9-12) • Proportion of women choosing follow-up care at the LSU GYN resident clinic versus transition to a local PrEP provider • Proportion of women initiating PrEP at the LSU resident GYN clinic who complete their first follow-up PrEP care visit (can only assess at the LSU GYN resident clinic or UMC PrEP clinic) • LDH navigator logs (number of contacts, number of appointments made through the PrEP navigator)

6. Data collection

Chart reviews, use of electronic medical records, and provider surveys

For baseline data collection (Phase 1, months 1-4), we will retrospectively collect data at the LSU GYN resident clinic, Tulane Downtown GYN Clinic, and the LSU PrEP clinic at the end of Phase 1 for the previous 4 months. Data will consist of the number of new PrEP prescriptions per month (overall among women and number of Black cisgender women specifically). No identifiable data will be collected. We may also collect baseline data for up to 12 months prior to Phase 2 initiation to compare trends over time.

Because the number of PrEP prescriptions among women at the Tulane Downtown GYN clinic and the Tulane PrEP clinic is extremely low, we will administer a survey to clinic leadership or another representative to gather the aggregate, de-identified data throughout implementation of this study. We will not access patient records at these sites. To collect data from the UMC PrEP clinic, in which [name] (study PI) is a provider, we will collect the de-identified data via provider survey if feasible (since numbers are also low), or if necessary, through patients' electronic medical records (EMR).

We will continue to collect data on PrEP prescriptions at the Tulane Downtown GYN Clinic, the Tulane PrEP clinic, and the LSU PrEP clinic until the end of Phase 3.

For data collection during the implementation phase (Phases 2 and 3, months 5-12) at the LSU GYN resident clinic, we will collect the number of new PrEP initiation counts for cisgender

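### The third primary comparison is meant to show trends outside the GYN clinics, but its sums include both GYN clinics and no Table 2 outcome isolates starts at the PrEP clinics

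*Protocol*

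**What the plan says.** Protocol section 5, Table 2, lists three primary clinical outcomes. The first is the number of women starting PrEP at the LSU GYN clinic in Phase 1 against Phases 2 and 3. The second compares the LSU GYN change "with the difference in patient numbers during the same time frame at the Tulane GYN clinic". The third takes LSU GYN and UMC PrEP together and compares their change with that of Tulane GYN and Tulane PrEP, "combined during the same time frame to further investigate trends outside of the GYN clinics potentially impacted by the social media campaign". Definition and purpose thus stand in one sentence.

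Section 4 says that the comparator arm serves to assess secular trends and "increases due to the social media campaign". Only LSU GYN receives the combined-care model, in Phase 2 and again in Phase 3. The campaign starts in Phase 3 and covers the whole New Orleans area.

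On volumes, section 6 expects about 30 eligible LSU GYN patients per week, "of which we anticipate ~2 will be initiated per week", so that over eight months "around 70 will take up PrEP in the GYN clinic". It gives no counts for the other clinics. It describes prescribing to women at the two Tulane clinics as extremely low and proposes a provider survey for the UMC PrEP clinic "since numbers are also low".

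Section 8 analyses the primary outcomes by difference-in-differences, LSU versus Tulane. It adds a Poisson regression of weekly starts across periods and sites with a product term.

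**The concern.** The purpose and the measure in the third bullet do not match. The purpose concerns clinics other than the GYN clinics. The measure adds a GYN clinic to each side, and on the LSU side that clinic is expected to supply most of the starts. It is also the only clinic that receives the other intervention. The first two bullets already cover LSU GYN. The secondary outcomes cover LSU GYN patients and the navigator logs. None reports starts at the UMC PrEP or Tulane PrEP clinic.

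The main risk is misattribution: a rise in the pooled figure against Phase 1 could be reported as demand created by the campaign outside the GYN clinics when the combined-care model produced it. A second, smaller risk is lost precision when Phase 3 is compared with Phase 2.

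**Working it through.** **Inputs from the protocol.** About 2 LSU GYN starts per week and about 70 in eight months (section 6); phases of four months (section 4).

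**Assumptions, because the protocol gives no figures.** LSU GYN baseline g of 0 to 5 starts in Phase 1; UMC PrEP count u of 3 to 10 per phase before the campaign; a doubling at UMC PrEP in Phase 3; each Tulane clinic steady at 1 per phase; Poisson counts; two-sided 5% level.

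**The plan's own figure.** Eight months = 8 × 52/12 = 34.7 weeks. 2 × 34.7 = 69.3, which agrees with about 70. Per four-month phase: 2 × 17.33 = 34.7 starts.

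**Phase 3 versus Phase 1.** Pooled difference-in-differences = (34.7 − g) + UMC PrEP change − Tulane changes.
- No change at any PrEP clinic: 34.7 − 0 = 34.7 and 34.7 − 5 = 29.7. In a Poisson simulation (200,000 draws, Wald test, u from 1 to 10) this was significant in 97 to 100% of draws.
- UMC PrEP doubles, u = 3, g = 0: LSU GYN supplies 34.7 / 37.7 = 92% of the pooled change.
- UMC PrEP doubles, u = 10, g = 5: LSU GYN supplies 29.7 / 39.7 = 75%.

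**Phase 3 versus Phase 2.** A steady LSU GYN level contributes 34.7 − 34.7 = 0 to the expected change, but 2 × 34.7 = 69.3 to its variance. With the Tulane terms left out:
- SE, UMC PrEP alone = √(u + 2u) = √(3u)
- SE, pooled = √(69.3 + 3u)

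| u | SE alone | SE pooled | Ratio | z alone | z pooled |
|---|---|---|---|---|---|
| 3 | 3.0 | 8.9 | 3.0 | 1.0 | 0.3 |
| 5 | 3.9 | 9.2 | 2.4 | 1.3 | 0.5 |
| 10 | 5.5 | 10.0 | 1.8 | 1.8 | 1.0 |

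The planned contrast also carries Tulane variance. At 1 start per Tulane clinic per phase, this adds 2 to the PrEP-only variance and 4 to the pooled variance. The ratio becomes √82.3 / √11 = 2.7 at u = 3 and √103.3 / √32 = 1.8 at u = 10, so the picture hardly changes.

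Simulated chance of detecting the doubling, with Tulane included:

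| u | PrEP clinics only | Pooled as written |
|---|---|---|
| 3 | 13% | 6% |
| 5 | 23% | 8% |
| 10 | 43% | 17% |

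**Recoverability.** Write D for a clinic's change in counts. Third bullet minus second = [(D LSU GYN + D UMC PrEP) − (D Tulane GYN + D Tulane PrEP)] − [D LSU GYN − D Tulane GYN] = D UMC PrEP − D Tulane PrEP.

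**The case against.** The bullet can be read as an extension of the second: add each system's PrEP clinic and see what changes. LSU GYN is also a plausible destination for women whom the campaign reaches, since the navigator refers them to a provider of their choice (section 3). A system total is therefore a sensible description of demand. The PrEP-clinic contrast can be obtained on the count scale by subtraction. The Poisson model compares sites, and the navigator logs record contacts and appointments directly. This is a pilot seeking initial indicators, with no power claim.

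Much of this stands. It supports keeping the pooled total, and it shows that the information is not lost. It does not make the sum a measure of trends outside the GYN clinics. The protocol never names the subtracted contrast. Section 8 describes the sites as LSU versus Tulane, so the regression cannot be relied on to separate clinics. The navigator logs count contacts and appointments, not PrEP starts. An analysis plan could add a breakdown by clinic, but the mismatch lies in how the protocol itself defines a primary outcome.

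A reader might infer that pooling hides a campaign effect that the PrEP clinics alone would reveal. The figures do not support that. For a doubling, z in UMC PrEP alone is √(u/3). It reaches 1.96 only at u of about 11.5, outside the assumed range. Small counts are the main limit, and pooling makes it worse.

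**Conclusion.** The point holds as a mismatch between the stated purpose of a primary outcome and its definition. The more serious consequence is in comparisons with Phase 1: an increase of about 30 to 35 starts is expected from the combined-care model alone, under an assumed LSU GYN baseline of 0 to 5 and the protocol's forecast of about 35 starts per phase. For Phase 3 versus Phase 2 the harm is added noise and not a shifted mean, with a standard error roughly 1.8 to 3.0 times larger.

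That ratio and the percentage shares rest on assumed PrEP-clinic counts, which the protocol describes only as low or extremely low. The direction holds across the range examined. It would go too far to say that the comparison has no use or that the PrEP-clinic signal cannot be recovered. The wording should be corrected, because followed as written it can yield a misattributed primary result.

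**What to change.** In Table 2, third primary bullet:
- Define the comparison on the PrEP clinics alone: the UMC PrEP change versus the Tulane PrEP change, as a difference-in-differences.
- Report each clinic's counts by phase, with Phase 3 versus Phase 2 as the campaign comparison and Phase 2 versus Phase 1 as the pre-campaign trend. Each clinic's own change is needed because the area-wide campaign may also reach Tulane, and a shared rise would cancel in the difference.
- Keep the pooled system totals as descriptive only.

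In section 6, name the Tulane PrEP clinic in the Phase 1 collection list. That list names the two GYN clinics and the LSU PrEP clinic only, although section 4 promises a baseline for local PrEP clinics and section 6 later speaks of continuing collection at Tulane PrEP.

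The cost is a few lines of protocol wording and one confirmed baseline count from a clinic that is to be surveyed anyway. The downside is that estimates from such small counts will be imprecise. They should be presented as descriptive pilot indicators.
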